## DOCUMENT HISTORY

Document	Date	Overall Rationale
Original Protocol	21JUL2023	Not applicable
Amendment 1	09FEB2024	Updated eligibility criteria, removed MQOL questionnaire, and updated questionnaire time points

## STATEMENT OF COMPLIANCE

The trial will be conducted in accordance with International Conference on Harmonization Good Clinical Practice (ICH GCP), applicable United States (US) Code of Federal Regulations (CFR). The Principal Investigator will assure that no deviation from, or changes to the protocol will take place without prior agreement from the Investigational New Drug (IND) or Investigational Device Exemption (IDE) sponsor, funding agency and documented approval from the Institutional Review Board (IRB), except where necessary to eliminate an immediate hazard(s) to the trial participants. All personnel involved in the conduct of this study have completed Human Subjects Protection and ICH GCP Training.

The protocol, informed consent form(s), recruitment materials, and all participant materials will be submitted to the IRB for review and approval. Approval of both the protocol and the consent form must be obtained before any participant is enrolled. Any amendment to the protocol will require review and approval by the IRB before the changes are implemented to the study. All changes to the consent form will be IRB approved; a determination will be made regarding whether a new consent needs to be obtained from participants who provided consent, using a previously approved consent form.

## ABREVIATIONS

Abbreviation	Definition/Explanation
ACI	As clinically indicated
AE	Adverse event
ALT	Alanine aminotransferase
ASCO	American Society of Clinical Oncology
AST	Aspartate aminotransferase
AV	Atrioventricular
BCVA	Best-corrected distance visual acuity
BICR	Blinded Independent Central Review
β-HCG	Beta-human chorionic gonadotropin
BID	Twice daily
BMI	Body mass index
BP	Blood pressure
BUN	Blood urea nitrogen
CBC	Complete blood count
CFR	Code of Federal Regulations
CHF	Congestive heart failure
CI	Confidence interval
CLIA	Clinical Laboratory Improvement Amendments
CL cr	Creatinine clearance
C max	Maximum observed concentration
C min	Trough observed concentration
CMP	Comprehensive metabolic panel
CNS	Central nervous system
CR	Complete response
CRF	Case report form
CT	Computed tomography
CTCAE	Common Toxicity Criteria for Adverse Events
ctDNA	Circulating tumor DNA
CYP	Cytochrome P450
CQ	Chloroquine

Abbreviation	Definition/Explanation
DILI	Drug-Induced Liver Injury
DoR	Duration of Response
DSMB	Data Safety Monitoring Board
ECOG	Eastern Cooperative Oncology Group
eCRF	Electronic case report form
ECG	Electrocardiogram
Eg	Exempli Gratia (for example)
FDA	Food and Drug Administration
GCP	Good Clinical Practice
GFR	Glomerular filtration rate
GGT	Gamma-glutamyltransferase
GI	Gastrointestinal
GMP	Good Manufacturing Practice
HBsAg	Hepatitis B surface antigen
HBV	Hepatitis B virus
HCV	Hepatitis C virus
HIV	Human immunodeficiency virus
HR	Heart rate
i.e.	Id est (that is)
IEC	Independent ethics committee
IND	Investigational New Drug
INR	International normalized ratio
IRB	Institutional review board
LDH	Lactate dehydrogenase
MRI	Magnetic resonance imaging
NIH	National Institute of Health
KAP	Ketamine-assisted Psychotherapy
PD	Pharmacodynamic(s)
PDAC	Pancreatic Ductal Adenocarcinoma
PFS	Progression-Free Survival
PK	Pharmacokinetic(s)

---

Abbreviation	Definition/Explanation
PO	Per os (administered by mouth)
PR	Partial response
PT	Prothrombin time
PTT	Partial thromboplastin time
QTc	QT interval corrected
QTcF	QT interval corrected using Fredericia equation
RBC	Red blood cell
RP2D	Recommended Phase 2 Dose
SAE	Serious adverse event
SD	Stable disease
SD-OCT	Spectral-domain ocular coherence tomography
T 1/2	Terminal elimination half-life
TdP	Torsades de Pointes
T max	Time of maximum observed concentration
ULN	The upper limit of normal
VF	Visual field
WBC	White blood cell

## 1 PROTOCOL SUMMARY

[figure not shown]
### 1.1 Synopsis

Title:	TREK: Ketamine-assisted Psychotherapy (KAP) for Patients with Existential Distress associated with Non-operable GI Cancers
Protocol Short Title	TREK
Study Description:	Open label, Pilot
Phase:	Pilot
Objectives:	
Primary Objective:  To assess the feasibility of recruiting, consenting, enrolling, and completing the study intervention in 12 patients.
 
Secondary Objectives:  To assess the safety and tolerability of ketamine-assisted therapy in the study population.  To determine the prevalence of existential distress in patients with non-operable GI cancers.

Endpoints:	
Primary Endpoint:  The recruitment, consent, enrollment, and study completion of 12 patients. Study completion defined as participating in at least 2/3 of the 3 KAP sessions.
 
Secondary Endpoints:  The frequency of adverse events (AEs) and serious adverse events (SAEs) characterized by type, severity (as defined by the NIH CTCAE, version 5.0), seriousness, duration, and relationship to study treatment.  The proportion of screened patients that meet criteria on the Existential Distress Scale (EDS: Single domain <math>\geq 3</math> or total score <math>\geq 6</math>)

Study Population:	
Key Inclusion Criteria:
 
 
Subjects with non-operable GI cancers who requiring multi-modal treatment (e.g. surgery +/- chemo +/-radiation) and have a high likelihood of recurrence and/or treatment failure in the opinion of the treating investigator
 

	
 
• Screen positivity for existential distress on the EDS, defined as scoring <math>\geq 3</math> on any of the 10 component domains, or a total score <math>\geq 6</math>
 
• ECOG Performance Status <math>\leq 2</math>.
 
 
Key Exclusion Criteria:
 
 
• Personal history or first- or second-degree relatives with schizophrenia, bipolar affective disorder, delusional disorder, schizoaffective disorder, psychosis, or other psychotic spectrum illness.
 
• Currently meeting DSM-5 criteria for Dissociative Disorder, or other psychiatric conditions judged to be incompatible with the establishment of rapport or safe exposure to ketamine.
 
• Currently meeting DSM-5 criteria for Cluster B Personality Disorder.
 
• Severe depression requiring immediate standard-of-care treatment (e.g., hospitalization).
 
• Suicidal ideation over the past month as assessed as a yes to question 3, 4, or 5 on the Columbia-Suicide Severity Rating Scale, Suicidal Ideation section
 
• Cancer with known CNS involvement, previously treated brain metastasis, or other major CNS disease.            Current or history within the last two years of meeting DSM-V criteria of substance use disorder (excluding caffeine and nicotine). Current substance use disorders may be identified through the drug urine screening test.
 
• Congestive heart failure, including all New York Heart Association Classes.
 
• Angina pectoris, cardiac hypertrophy, cardiac ischemia, myocardial infarction
 
• Uncontrolled hypertension at the time of enrollment (BP<math>>140</math> systolic or 90 diastolic), coronary artery disease, artificial heart valve
 
• Prolonged or congenital long QT syndrome (<math>>450</math> ms), serious cardiac arrhythmias, tachycardia, a clinically significant screening ECG abnormality
 
• History of hypersensitivity to ketamine
 
• Receiving ketamine treatments for psychiatric condition within the past 6 months
 
• Seizure disorder
 
• Moderate to severe dementia
 
• History of significant traumatic brain injury
 
• Requires the use of supplemental oxygen.
 

--	---

	
 
Any other condition that would, in the Investigator's judgment, contraindicate the subject's participation in the clinical study due to safety concerns or compliance with clinical study procedures (e.g., infection/inflammation, intestinal obstruction, unable to swallow medication, [patients may not receive the drug through a feeding tube], social/ psychological issues, etc.)
 
Subjects taking prohibited medications. A washout period of prohibited medications for a period of at least five half-lives should occur prior to study registration. These medications include antipsychotic medications, doses of benzodiazepines in excess of 20mg diazepam equivalents per day.
 

Study Intervention:	Ketamine, 0.5-1.2mg/kg, IM
Study Duration:	1 year
Participant Duration:	6 months

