## 5 STUDY POPULATION

Potential study participants must meet all inclusion criteria and no exclusion criteria to be deemed eligible for trial participation. To ensure subject safety, all subjects must be deemed eligible at the time of study registration and must continue to meet eligibility criteria up to ketamine dosing. This eligibility checklist is used to determine subject eligibility and will be filed with the enrolling investigator's signature in the subject research chart.

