### 5.1 Inclusion Criteria

1.  Subject aged  $\geq$  18 years.
2.  Subjects with non-operable GI cancers requiring multi-modal treatment (e.g. surgery +/- chemo +/-radiation) and have a high likelihood of recurrence and/or treatment failure in the opinion of the treating investigator.
3.  Screen positivity for existential distress on the EDS, defined as scoring  $\geq$  3 on any of the 10 component domains, or a total score  $\geq$  6
4.  ECOG Performance Status  $\leq$  2.
5.  Adequate hepatic function as defined as:
  - Total Bilirubin  $\leq$  1.5x institutional upper limit of normal (ULN) unless elevated bilirubin is related to Gilbert's Syndrome
  - AST(SGOT)/ALT(SGPT)  $\leq$  3  $\times$  institutional ULN
    - Subjects with liver metastases will be allowed to enroll with AST and ALT levels  $\leq$  5  $\times$  ULN.
6.  For subjects of childbearing potential: Negative pregnancy test or evidence of post-menopausal status. The post-menopausal status will be defined as having been amenorrheic for 12 months without an alternative medical cause. The following age-specific requirements apply:
  - Subjects  $<$  50 years of age:
    - Amenorrheic for  $\geq$  12 months following cessation of exogenous hormonal treatments; and
    - Luteinizing hormone and follicle-stimulating hormone levels in the post-menopausal range for the institution; or
    - Underwent surgical sterilization (bilateral oophorectomy or hysterectomy).
  - Subjects  $\geq$  50 years of age:
    - Amenorrheic for 12 months or more following cessation of all exogenous hormonal treatments; or
    - Had radiation-induced menopause with last menses  $>1$  year ago; or

- Had chemotherapy-induced menopause with last menses >1 year ago; or
- Underwent surgical sterilization (bilateral oophorectomy, bilateral salpingectomy, or hysterectomy).

7.  Subjects of childbearing potential and subjects with a sexual partner of childbearing potential must agree to use a highly effective method of contraception as described in Section 5.3.1.

8.  Subjects with a sexual partner of childbearing potential must agree to use a condom during intercourse for 24 hours post- ketamine dose.

9.  Agree to refrain from using any psychoactive drugs, including alcoholic beverages, ondansetron, cannabis, and non-routine PRN medications within 24 hours of each ketamine administration. Exceptions include daily use of caffeine, nicotine, and opioid pain medication (see Section 6.5.1).

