10.  Able to provide informed consent and willing to sign an approved consent form that conforms to federal and institutional guidelines.

11.  Agree that for one week preceding the ketamine session, he/she will refrain from taking any nonprescription medication, nutritional supplement, or herbal supplement except when approved by the research team. Exceptions will be evaluated by the research team and will include acetaminophen, non-steroidal anti-inflammatory drugs, and common doses of vitamins and minerals.

12.  Agree not to use nicotine for at least 2 hours before the ketamine administration or for the duration of the ketamine session.

13.  Agree to consume approximately the same amount of caffeine-containing beverage (e.g., coffee, tea) that he/she consumes on a usual morning, before arriving at the research unit on the morning of the ketamine session. If the subject does not routinely consume caffeinated beverages, he or she must agree not to do so on the day of ketamine administration.

14.  Subjects requiring opioid use for pain are on a stable pain management regimen or do not experience clinically significant sedation during opioid use.

- Note: Long-acting opioid medications (e.g., oxycodone sustained-release, morphine sustained release) will be allowed if the last dose occurred at least 6 hours before ketamine administration; such medication will not be taken again until at least 6 hours after ketamine administration.

15.  Fluent in English.

16.  Reading literacy and comprehension sufficient for understanding the consent form and study questionnaires, as evaluated by study staff obtaining consent.

17.  Have a support person who is be able to escort the subject home from the ketamine dosing sessions.

- Note: The use of ride services will not be permitted (e.g., Uber, Lift, taxi, etc.)

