- Any other condition that would, in the Investigator's judgment, contraindicate the subject's participation in the clinical study due to safety concerns or compliance with clinical study procedures (e.g., infection/inflammation, intestinal obstruction, unable to swallow medication, [subjects may not receive the drug through a feeding tube], social/ psychological issues, etc.)

10.  Known HIV infection with a detectable viral load within 6 months of the anticipated start of treatment.

Note: Subjects on effective antiretroviral therapy with an undetectable viral load within 6 months of the anticipated start of treatment are eligible for this trial.

11.  Active infection including tuberculosis (clinical evaluation that includes clinical history, physical examination, radiographic findings, and TB testing in line with local practice), hepatitis B (known positive HBV surface antigen (HBsAg) result), or hepatitis C.

Note: Subjects with a past or resolved HBV infection (defined as the presence of hepatitis B core antibody [anti-HBc] and absence of HBsAg) are eligible. Subjects positive for hepatitis C (HCV) antibody are eligible only if polymerase chain reaction is negative for HCV RNA.

12.  Medical, psychiatric, cognitive, or other conditions that may compromise the subject's ability to understand the subject information, give informed consent, comply with the study protocol or complete the study.

13.  Known prior severe hypersensitivity to ketamine or any component in its formulations (NCI CTCAE v5.0 Grade ≥ 3).

14.  Subjects taking prohibited medications as described in Section 6.5.1. A washout period of prohibited medications for a period of at least five half-lives or as clinically indicated should occur before the start of treatment.

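### Antipsychotics are excluded by name only in the synopsis: exclusion 14 cites a missing section, and its evident target, Section 6.6.1, omits them and is inconsistent on opioids and benzodiazepines

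*Combined protocol and SAP*

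**What the plan says.** **Synopsis (1.1, Key Exclusion Criteria).** Patients on prohibited medications are excluded, with the drugs given as "These medications include antipsychotic medications, doses of benzodiazepines in excess of 20mg diazepam equivalents per day". On timing: "A washout period of prohibited medications for a period of at least five half-lives should occur prior to study registration".

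**Section 5.** The lists in 5.1 and 5.2 are the working instrument: "This eligibility checklist is used to determine subject eligibility", and the signed copy is filed. On timing, "all subjects must be deemed eligible at the time of study registration and must continue to meet eligibility criteria up to ketamine dosing". Section 5.3 likewise requires all eligibility requirements to be met before registration.

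**Exclusion 14 (5.2).** "Subjects taking prohibited medications as described in Section 6.5.1" is the whole of its drug content. Its washout is also five half-lives, but it adds a clinical-indication alternative and counts to the start of treatment.

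**Opioids at entry (5.1).** Inclusion 9 asks for 24 hours without psychoactive drugs, alcohol included, around each dose, then says: "Exceptions include daily use of caffeine, nicotine, and opioid pain medication (see Section 6.5.1". Inclusion 14 reads "Subjects requiring opioid use for pain are on a stable pain management regimen or do not experience clinically significant sedation during opioid use", and its note says that long-acting opioids "will be allowed if the last dose occurred at least 6 hours before ketamine administration". The closing paragraphs of Section 6.2.4 repeat the 6 hours and the 24-hour psychoactive-drug rule.

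**Section 6.6.1.** During treatment it prohibits whatever the exclusion criteria specifically prohibit, plus a list that includes MAO inhibitors and, under sedatives, all opioids, benzodiazepines, sedative hypnotics and alcohol. It then sets a 12-hour pre-dose hold on long-acting opioids for patients taking them.

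**Section 6.2.2.** The pre-dose medication check covers sedatives and psychostimulants (12 hours) and MAO inhibitors (2 weeks).

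A block of text between the end of the exclusion list and Section 5.3 was not available for this review. Exclusion 14 reads as complete without it.

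**The concern.** A named safety exclusion should appear on the form that staff sign. Here the name is in the synopsis, while the checklist defers to a section that cannot be found. Someone working from the checklist alone could register a patient on an antipsychotic without meeting any line that names the class or triggers its washout.

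Resolving the reference to Section 6.6.1 does not cure this and brings new difficulties. That section was written for the treatment phase, and its entries on opioids, benzodiazepines and alcohol do not fit the entry rules. Staff could reach different decisions about the same patient depending on which section they open, on the dosing day as well as at entry. The oversight plan in Section 8.4 classes the trial as high risk, and only 12 patients will be enrolled.

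**Working it through.** No sample size, power or event figure is involved. The check is a comparison of texts.

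**1. Does Section 6.5.1 exist?** No. Section 6.5 is one sentence on supportive care, without subsections. It is cited as 6.5.1 in three places: inclusion 9, exclusion 14 and Section 7.1.4. Other Section 6 references are shifted by one in the same way: the Schedule of Events footnotes cite 6.1.2 and 6.1.3 for content now in 6.2.2 and 6.2.3, and Section 6.4 cites 6.1.4 for content now in 6.2.4. So 6.5.1 almost certainly means 6.6.1.

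**2. Where are antipsychotics covered?**

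| Place | Governs | Antipsychotics named? | Time off drug |
|---|---|---|---|
| Synopsis | Entry | Yes | Five half-lives, before registration |
| Exclusion 14 | Entry | No | Five half-lives or clinical indication, before treatment |
| Section 6.2.2 | Each dose | No | 12 h for sedatives and psychostimulants; 2 weeks for MAO inhibitors |
| Section 6.6.1 | Treatment phase | No | None stated for this class |
| Inclusion 9, Section 6.2.4 | Each dose | Not by name (psychoactive drugs) | 24 h |

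The opening sentence of 6.6.1 could bring in the synopsis exclusion for the treatment phase. Within Section 5, however, it leads back to exclusion 14, which names nothing, so the reference is circular.

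**3. Opioids.** Section 6.6.1 bans them and also tells patients who take them when to stop. Inclusions 9 and 14 and Section 6.2.4 allow them. The pre-dose hold on long-acting opioids is 12 h in 6.6.1 and 6 h in inclusion 14 and 6.2.4, a difference of 12 − 6 = 6 h. A patient whose last long-acting dose was between 6 and 12 hours before the injection satisfies two texts and breaches the third. If 6.2.2 is read with the 6.6.1 grouping of opioids as sedatives, its 12-hour check would also stop a patient on a permitted daily opioid.

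**4. Benzodiazepines.** The synopsis limit is above 20 mg diazepam equivalents per day; 6.6.1 has no threshold. The mismatch covers doses above 0 and up to 20 mg per day. Section 6.6.1 also has no exemption for the on-demand lorazepam of Section 6.2.4 (0.5 mg, repeatable once).

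**5. Washout anchor.** Section 5 and Section 5.3 both require eligibility at registration, which agrees with the synopsis. The later anchor and the softer wording in exclusion 14 are the only text out of line.

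**6. Would changing 6.5.1 to 6.6.1 be enough?** No. Antipsychotics would still be missing, and the whole 6.6.1 list would become an entry criterion with a washout. That would catch alcohol users and opioid users whom inclusions 9 and 14 admit.

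**The case against.** The strongest reply is that the checklist is not silent. Inclusion 9 bars psychoactive drugs for 24 hours around each dose, which on ordinary reading covers antipsychotics and benzodiazepines. Exclusion 2 removes patients with a personal or family history of psychotic or bipolar illness. Exclusion 12, the psychiatric evaluation, medication review and investigator judgment add further cover. This stands as mitigation, and a reader should not infer that an antipsychotic user would pass unnoticed. But 24 hours is not a five-half-life washout, exclusion 2 concerns diagnosis and not drug use, and none of the other checks names the class.

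Two further inferences go beyond the text. One is that 6.6.1 shuts out all opioid users; its own timing rules for such patients show that it expects them on treatment, so the fault is inconsistency and not a clear ban. The other is that the synopsis expressly admits benzodiazepine doses of 20 mg per day or less; its list is introduced as an inclusive one and only implies this, and 6.6.1 addresses the treatment phase.

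It can also be said that the synopsis may be the stale text. The Document History records that Amendment 1 updated the eligibility criteria, and Section 5.2 is narrower than the synopsis elsewhere: unstable angina against any angina, myocardial infarction within 3 months against no limit, Grade 3 or higher hypersensitivity against any. This is a fair point. The documents do not settle it, so the fix must leave the sponsor that choice.

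Finally, the dead reference is clerical and easily resolved. That is true of the section number, but step 6 above shows that correcting the number alone does not repair the content.

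**Conclusion.** The point holds as an internal inconsistency with a bearing on patient safety. In the text available, a stated exclusion is named in the synopsis and in none of exclusion 14, Section 6.2.2 or Section 6.6.1. Three references lead to a section that does not exist. The long-acting opioid hold differs by 6 hours between sections, and benzodiazepine doses above 0 and up to 20 mg diazepam equivalents per day are treated differently by the synopsis and by 6.6.1.

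This rests on two assumptions: that 6.5.1 was meant to be 6.6.1, and that the unavailable text adds nothing to exclusion 14. Whether the antipsychotic exclusion is still intended is for the sponsor to say; either way the two texts must agree. No number of affected patients can be derived from the documents, and nothing in the feasibility, safety, prevalence or exploratory analyses changes.

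**What to change.** 1. **Exclusion 14.** Name the entry-excluded drugs there: antipsychotics, and benzodiazepines above 20 mg diazepam equivalents per day, with the five-half-life washout finished before registration. Do not import the whole 6.6.1 list as an entry criterion. If the antipsychotic exclusion was dropped on purpose in Amendment 1, delete it from the synopsis instead.
2. **If it is kept,** add antipsychotics to the 6.6.1 list and to the 6.2.2 medication check.
3. **Benzodiazepines and alcohol.** In 6.6.1, limit benzodiazepines to the synopsis threshold, with none, and no alcohol, in the 24 hours before dosing set by inclusion 9 and 6.2.4. Bring the 12-hour sedative check in 6.2.2 into line with that, and exempt lorazepam given under 6.2.4.
4. **Opioids.** Exempt the regimens allowed by inclusions 9 and 14 from the 6.6.1 ban and from the 6.2.2 sedative check. State one pre-dose hold for long-acting opioids in inclusion 14, 6.2.4 and 6.6.1: 6 h, or 12 h if the sponsor's clinicians prefer it.
5. **Last,** correct the remaining 6.5.1 references (inclusion 9 and Section 7.1.4) to 6.6.1.

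The cost is a wording amendment. No new data are needed: medication history is already taken before each dose (6.2.2), and concomitant medications are already recorded from 28 days before registration (6.6).
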